- Patients receiving 80 mg ixekizumab Q4W, who relapse, will continue on 80 mg ixekizumab Q4W in order to maintain the study blind and to evaluate the long term efficacy of ixekizumab treatment.
- Patients receiving placebo who relapse will be switched to 80 mg ixekizumab Q4W.

Continued treatment for patients who relapse is provided to understand the longer-term efficacy of ixekizumab when treating patients who experience relapse and to maintain study blinding. See Section 8.3.1 for discontinuation criteria.

**Treatment Assignment for Non-Responders:** Patients randomized to ixekizumab at Week 0 (Period 2) who are non-responders at Week 12 (Visit 7) will receive treatment with 80 mg ixekizumab Q4W during Period 3.

Patients randomized to placebo at Week 0 (Period 2) who are non-responders at Week 12 (Visit 7) will receive treatment with 80 mg ixekizumab Q4W during Period 3. These patients will receive a starting dose of 160 mg ixekizumab as 2 SC injections at Week 12 (Visit 7).

Continued treatment for non-responders is provided so that partial or slow responders to ixekizumab and non-responders to placebo may remain in the study and receive treatment with ixekizumab while maintaining the study blind. Some patients may be deriving benefit from treatment with ixekizumab but will be slow responders or partial responders thereby not meeting the “responder” criteria at Week 12. A discontinuation criterion for patients who remain at or above their baseline sPGA score at both Week 12 and Week 24 is included (see Section 8.3.1) to ensure that patients who have not shown any benefit from treatment with ixekizumab can be treated with any other psoriasis therapy as determined appropriate by the investigator.

Once a patient has switched to 80 mg Q4W, regardless of original treatment in Period 2, re-randomization in Period 3, or any assessments of response/relapse, the patient will remain on 80 mg Q4W.

Patients who discontinue the study for any reason during Period 3 will stop treatment and continue to the ETV prior to entering the Post-Treatment Follow-Up Period (Period 4; Section 7.1.4).

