#### **10.3.2.6. Safety-Related Immune Markers**

IL-17 is believed to play a role in neutrophil homeostasis and in neutrophil-dependent host defense against extracellular infections (Happel et al. 2003; Huang et al. 2004; Milner et al. 2008). Neutrophil counts will therefore serve as a safety marker in the current investigation.

Ixekizumab is not expected to affect the numbers of B, T, and natural killer (NK) lymphocytes or serum immunoglobulin subclasses A, G, and M (IgA, IgG, and immunoglobulin M [IgM], respectively) in peripheral blood. However, since this is a novel immunomodulatory drug, these parameters will be measured in patients.

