6.1.2. General Considerations for Analyses during Period 2 (Induction Dosing Period)

Period 2 starts after the first dose of study treatment (Visit 2, Week 0) and ends prior to the first injection of study treatment at Week 12 (Visit 7) or the early discontinuation visit (between Weeks 0 and 12). If a patient has Visit 7 but does not receive injection at Week 12 (Visit 7), the last recorded time for Visit 7 is used as the end time for Period 2.

Baseline for ITT and Safety Populations will be defined as the last available value before the first injection for efficacy, health outcomes, and safety analyses. In most cases, this will be the measure recorded at Week 0 (Visit 2). For efficacy/health outcome measures, if the patient does not take any injection, the last available value on or prior to randomization date will be used. Change from baseline (CFB) will be calculated as the visit value of interest minus the baseline value. For safety analyses using a baseline period, the baseline period is defined as the time from Visit 1 to the date/time of the first injection.

Comparisons between each ixekizumab treatment group (80 mg Q2W or 80 mg Q4W) and placebo will be performed for all analyses in Period 2.

The primary analysis method for treatment comparisons of categorical efficacy and health outcomes variables will be a logistic regression analysis with treatment as a factor using PROC Logistic. The odds ratio and the corresponding 95% CIs, as well as the treatment differences and the corresponding 95% CIs, will be reported. Secondary analysis will be conducted using a Fisher's exact test. In the case when logistic regression model does not produce statistical results due to sparse data, Fisher's exact test will be used.

For all categorical efficacy and health outcome variables that are collected at repeated visits, treatment group comparisons will be analyzed at each visit using the logistic regression model. Missing data will be imputed using the NRI method (Section 6.2.1).

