6.12.2. Adverse Events

Adverse events (AEs) will be classified based upon the latest version of the MedDRA. Any condition starting on or after the date of informed consent will be considered an AE. Any preexisting condition which worsens in severity on or after the date of informed consent will be considered and recorded as an AE on the *Adverse Event (AE)* eCRF page from the date of worsening onwards.

A treatment-emergent adverse event (TEAE) is defined as an event that first occurred or worsened in severity after baseline and on or prior to the date of the last visit within the defined treatment period. Both the date/time of the event and the date/time of the dose (that is, injection) are considered when determining TEAEs. Treatment-emergent AEs will be assigned to the study period to which it’s considered treatment-emergent:

- The MedDRA lowest level term (LLT) will be used when classifying AEs as treatment-emergent.
- The maximum severity recorded for each LLT prior to the first dose date/time in the treatment period will be used as the pre-treatment severity for that LLT. If an event during the baseline period has missing severity, and the event persists during the treatment period, then it will be considered as treatment-emergent, regardless of the post-baseline level of severity. Events with a missing severity during the treatment period will be considered treatment-emergent.
- AEs with a particular LLT will be classified as treatment-emergent if they first start on or after the first dose date/time in the treatment period (i.e., a patient has no preexisting conditions with that lowest level term), or if the severity is greater than the pre-treatment severity for that lowest level term. If a partial AE start date/time is present, the date/time

will be compared as far as possible to the treatment start date/time in order to determine whether the event is treatment-emergent or not. If there is any doubt, the event will be flagged as treatment-emergent.

A follow-up emergent adverse event (FEAE) is defined as an event that first occurred or worsened in severity after the date of Visit 19 (that is, Week 60) or the ETV:

- The MedDRA LLT will be used when classifying AEs as follow-up emergent.
- For AEs that are ongoing at the date of Visit 19 or ETV, the maximum severity recorded for each LLT on or prior to the date of Visit 19 or ETV will be used as the follow-up baseline severity for that LLT.

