Adverse events and TEAEs will be summarized for the following time periods and analysis populations:

- Period 2 (Safety Population)
- Period 3 (Maintenance Dosing Period Primary/Secondary/Relapse Population)
- Period 4 (Follow-up Population)

An overall summary of AEs including the number and percentage of patients who experienced TEAE, TEAE by maximum severity, death, SAE, TEAE possibly related to study treatment, discontinuations from the treatment due to an AE, and TEAEs of special interest will be performed for Periods 2 (Safety Population) and 3 (Maintenance Dosing Period Primary/Secondary/Relapse Population).

The following summaries/analyses will be performed for Periods 2 (Safety Population) and 3 (Maintenance Dosing Period Primary Population), unless noted otherwise:

- TEAE by SOC and PT.
- TEAE by PT.
- TEAE by maximum severity, SOC, and PT.

Follow-up emergent AEs will be summarized for the Follow-Up Population in Period 4:

- FEAE by PT.

In general, for all AE-related summaries, the number and percentage of patients experiencing the events will be presented by treatment group. In general, events will be ordered by decreasing frequency in the total ixekizumab group, followed in the order of ixekizumab Q2W, ixekizumab Q4W, and placebo (when applicable) group, within SOC and/or PT for sorting. For events that are gender-specific (as defined by MedDRA), the denominator and computation of the percentage will include only patients from the given gender.

A by-patient listing of all AEs for safety population will be provided.

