Infections	
Infections are events including all infections (defined using all the MedDRA PTs from the Infections and infestations SOC), serious infections, potential opportunistic infections (OIs), and infections resulting in anti-infective medication administration (i.e., antibacterial, antiviral, antifungal, antiparasitic treatment).
 
Anti-infective medications are defined in the LY2439821 PSAP v8 Appendix 5 (or most current version) including antibiotics, antifungals, antivirals, or antiprotozoals. Listing of patients experiencing a TEAE of infections will be provided including the following additional information: anti-infective medications use (if treated) with medication start/end dates, indication for use, and route; minimum post-baseline value within treatment Period 2 for leukocytes, platelets, lymphocytes, and absolute neutrophils.
	
Period 2 (Fisher’s exact test), Period 3 (Fisher’s exact test for Maintenance Dosing Period Primary Population): SAE by PT, AE leading to treatment discontinuation by PT
 
Listing: TEAE with information collected on Infection eCRF page, TEAE with anti-infective medications.

Special Safety Topic	Definition / Derivation	Analysis / Summary / Listing
	
The list of MedDRA terms used to identify infections that are predefined as potential opportunistic infections (OI) are found in the LY2439821 PSAP v8 Appendix 10 (or most current version). This list contains PTs as contained within categories (narrow and broad) from the Infections and Infestations SOC and the Investigations SOC which can assist in identifying potential OIs. The narrow terms are considered OIs unless medical review determined the reported term is not consistent with the patient’s clinical history/presentation/course. Medical review of broad terms is needed for final determination of patients meeting the program definition of OIs.
 
Listing of patients experiencing a TEAE of OIs will be provided including the following additional information: source of identification (CRF or Lilly specified list), primary/secondary site of infection, primary/secondary infection type, primary/secondary identified by a laboratory diagnostic test (Yes/No), acquired in a Health care setting (Yes/No).
	
Period 2 (Fisher’s exact test), Period 3 (Fisher’s exact test for Maintenance Dosing Period Primary Population): TEAE of OIs by PT
 
Listing: TEAE of OIs.

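### The infection listing shows only Period 2 blood-count minima, so a Period 3 infection appears beside counts from the wrong period and often from a different treatment

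*SAP*

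**What the plan says.** The Infections row of Table RHBH.6.8 (SAP 6.12.3.1) plans the output in these terms: "Listing of patients experiencing a TEAE of infections will be provided including the following additional information". What follows is anti-infective medication details and the "minimum post-baseline value within treatment Period 2 for leukocytes, platelets, lymphocytes, and absolute neutrophils". No sentence limits the infections themselves to Period 2.

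The same row analyses infections in both dosing periods. Its output column includes "Period 3 (Fisher’s exact test for Maintenance Dosing Period Primary Population): SAE by PT, AE leading to treatment discontinuation by PT". SAP 6.12.2 assigns each treatment-emergent event to a study period and summarises events for the Period 3 Primary, Secondary and Relapse populations as well as for Period 2.

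Under SAP 6.1.2 and 6.1.3, Period 2 closes before the Week 12 injection, and Period 3 runs from that injection to Week 60 or early termination.

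Protocol 10.3.2.6 explains that IL-17 is thought to play a part in neutrophil-dependent defence against infection, and concludes: "Neutrophil counts will therefore serve as a safety marker in the current investigation".

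**The concern.** The events in the listing can come from either dosing period, but the counts beside them can come only from the first. A patient with a normal Period 2 minimum who is both neutropenic and infected in Period 3 would be listed with the normal value. Nothing in the specification tells the reader that the count may predate the infection by months.

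Treatment also changes for many patients at Week 12. Under Protocol 7.1.3, patients randomised to placebo "who are non-responders at Week 12 (Visit 7) will receive treatment with 80 mg ixekizumab Q4W during Period 3". Their Period 3 infections occur on ixekizumab, but the listed minimum was measured on placebo. Ixekizumab responders re-randomised to placebo have the reverse mismatch. A medical reviewer comparing counts by treatment could be misled in either direction.

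**Working it through.** **Step 1. Length of each period.** Inputs: Week 12 and Week 60 (Protocol Attachment 1, study days 84 and 420).
- Period 3: 60 − 12 = 48 weeks; in days, 420 − 84 = 336, and 336 / 7 = 48. This reproduces the 48 weeks stated on the protocol's opening page.
- Share of planned treatment time outside the count window: 48 / 60 = 80%.

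**Step 2. Scheduled haematology.** Input: the haematology rows of Attachment 1, post-baseline visits only. The Week 12 draw is assumed to precede the Week 12 injection and so to belong to Period 2.
- Period 2: Weeks 1, 2, 4, 8, 12 = 5 draws.
- Period 3: Weeks 16, 20, 24, 32, 40, 48, 60 = 7 draws.
- Scheduled draws that can never enter the listing: 7 / 12 = 58%.

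**Step 3. Patients whose treatment differs between the two periods.** Inputs: Protocol 12.1 and the synopsis.
- Placebo to ixekizumab at Week 12: 84 × (1 − 0.05) = 79.8, about 80. This assumes that nobody leaves before Week 12. As an illustrative lower figure, the synopsis plans 336 of 420 completers (80%). If all of that loss fell before Week 12, equally across groups, and the 5% responders (84 × 0.05 = 4.2) all stayed, then 84 × 0.80 − 4.2 = 63. The documents do not say when dropout is expected, so the range is about 63 to 80.
- Ixekizumab to placebo: 168 × 0.70 × 1/3 = 39.2 per induction regimen. This matches the planned 39, or 2 × 39 = 78 in total. They stay on placebo until relapse.
- The remaining ixekizumab patients stay on ixekizumab, so their listed counts are on-drug but from the wrong window for a Period 3 infection. For those induced on Q2W, the regimen has also changed.

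**Step 4. The SAP's convention elsewhere.**

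| SAP output | Window for the extreme value |
|---|---|
| Hepatic shifts (Table RHBH.6.8) | maximum within each study period |
| White cell and platelet shift tables (6.12.4.1) | minimum within each study period |
| Infection duration (Table RHBH.6.8, Infections) | Periods 2 and 3, infections beginning in that period |
| Infection listing (Table RHBH.6.8, Infections) | minimum within Period 2 only |

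The infection listing is the exception among these, and no reason is given.

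**The case against.** The strongest reply is that nothing is lost. SAP 6.12.4.1 gives shift tables to the minimum count for Periods 2 and 3, including unscheduled draws. SAP 6.12.4 plans a by-patient listing of abnormal results for leukocytes and platelets with no Period 2 limit. That wording matches the 6.12.4.1 heading, which also covers neutrophils and lymphocytes. Table RHBH.6.8 adds a by-patient listing of cytopenia events. A reader might infer from the Period 2 restriction that the study cannot connect infection with neutropenia after Week 12. The documents do not support that: the outputs can be cross-matched by patient. What remains is that none of them is tied to infection events, and the listing that does set counts beside infections sets the wrong ones for Period 3.

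Other objections stand in part:
- **Purpose.** Neither document says the listing is meant to link infection to neutropenia; the counts are described only as additional information. Even within Period 2, a period minimum need not precede the infection. This limits what the listing could show after correction, but does not justify a count from another period.
- **Intent.** Protocol 12.2.8 focuses the primary safety analyses on Period 2, so the slip could lie in the event scope and not in the count window. The text does not say so. If it was intended, Period 3 infections have no listing with counts, and the scope should be stated.
- **Unseen source.** SAP 6.12.3.1 lets the program safety analysis plan supersede this table. That plan is not available, so it may already differ; the SAP text would still need to agree with it.
- **Residual drug.** Protocol 7.2 gives a half-life of 13 days, so the treatment mismatch for responders moved to placebo is less sharp in the first weeks after Week 12.

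**Conclusion.** The point holds for the listing. As written, any infection starting in Period 3 is shown with a minimum count from Period 2, contrary to the within-period rule the SAP uses for its hepatic and blood-count shift tables. The period affected is 48 of 60 planned treatment weeks and 7 of 12 scheduled post-baseline draws. These are shares of time and of draws. A reader might take 80% as the share of infections or of patients affected, but the documents give no infection rates from which to work that out.

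The figure of about 80 of 84 placebo patients is an upper bound that rests on the assumed 5% response and no dropout before Week 12. The 78 responders moved to placebo rest on the planned 70% re-randomisation.

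This is a drafting inconsistency in descriptive safety output. It touches no test, estimate, alpha or power. It is worth correcting because infection and cytopenias are both adverse events of special interest (Protocol 10.3.1.1.1), and the column can mislead without any sign that it does so.

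**What to change.** In the Infections row of Table RHBH.6.8, replace the restriction to Period 2 with *within the study period in which the infection started*, meaning Period 2, Period 3 or the retreatment period defined in SAP 6.1.3.3. Add a column naming that period and the treatment then being received, so that the pairing is visible. If only Period 2 infections were intended, say so and state where Period 3 infections are listed with their counts. Check the program safety analysis plan for matching wording.

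The cost is one phrase in the SAP and a small programming change. The Period 3 haematology is already collected.

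Showing the last count on or before infection onset is optional. It would bring the count closer to the event, but scheduled draws after Week 24 are at Weeks 32, 40, 48 and 60. Without an unscheduled draw, that value could be up to about 8 weeks old, or 12 weeks old after Week 48, so its date should be shown.

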#### **10.3.1.1.1. Adverse Events of Special Interest**

The following adverse events of special interest (AESIs) will be used to determine the safety and tolerability of ixekizumab over the range of doses selected for this clinical study.

Adverse events of special interest for ixekizumab are:

- cytopenias (leukopenia, neutropenia, and thrombocytopenia)
- liver function test changes/enzyme elevations (ALT, AST, bilirubin, and ALP)
- infection
- injection-site reactions
- allergic reactions/hypersensitivities
- cerebro-cardiovascular events (potential and adjudicated endpoints)
- malignancies
- IBD (CD and UC)
- depression
- pneumocystis pneumonia (PCP) and interstitial lung disease (ILD).

If infections, injection-site reactions, allergic reactions/hypersensitivities or inflammatory bowel disease are reported, sites will provide details on these events as instructed on the CRF.

Investigators will also educate patients and/or authorized adults who have been trained about the symptoms of allergic reactions/hypersensitivities and will provide instructions on dealing with

these reactions. A blood sample will be collected when possible for any patient who experiences an AE of potential systemic allergic reactions/hypersensitivities during the study.

Data on preferred terms (PTs) that could potentially result in cerebro-cardiovascular events (defined as death, MI, stroke, hospitalization for unstable angina, hospitalization for heart failure, coronary revascularization procedure, peripheral revascularization procedure, cardiogenic shock due to MI, resuscitated sudden death, serious arrhythmia, hospitalization for hypertension, and peripheral arterial event) and associated events based on Medical Dictionary for Regulatory Activities (MedDRA). PT codes will be collected and the events will be adjudicated by an external Clinical Events Committee (CEC) made up of a chairman, 2 cardiologists, and a neurologist.

Data on suspected IBD, as identified by events possibly indicative of ulcerative colitis and CD, will be collected and the events will be adjudicated by an external CEC made up of gastroenterologists with expertise in IBD.

The role of the CECs is to adjudicate defined clinical events, in a blinded, consistent, and unbiased manner throughout the course of a study. The importance of the CECs is to ensure that a single group evaluates all events that have been reported uniformly.

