	
for confirmation of an event. All events which qualify for CEC adjudication will be used for the analysis of cerebro-cardiovascular events. The categories of adjudicated events used for the analysis will include the following:
 
 • Cardiovascular 
 ○ Death (Cardiovascular) ○ Myocardial Infarction (MI) ○ Hospitalization for Unstable Angina ○ Hospitalization for Heart Failure ○ Serious Arrhythmia ○ Hospitalization for Hypertension ○ Resuscitated Sudden Death ○ Cardiogenic Shock due to Myocardial Infarction ○ Coronary Revascularization Procedure • Neurologic 
 ○ Cerebrovascular Event: Transient Ischemic Attack or Stroke (Haemorrhagic, Ischemic and Undetermined) • Peripheral Vascular Events 
 ○ Peripheral Arterial Event ○ Peripheral Revascularization Procedure 
Events will be analyzed using MedDRA PT nested within the CEC assessment (confirmed event, no event, or insufficient documentation for event determination) and the subcategory. Subtypes of stroke (Hemorrhagic Stroke, Ischemic Stroke, and Undetermined Stroke Type) will be displayed in the analyses nested within stroke. Subcategories of Serious Arrhythmia (Atrial Arrhythmia, Ventricular Arrhythmia, Heart Block, Other, Unknown) will be displayed nested within Serious Arrhythmia.
	
TEAE

Major Adverse Cerebro-cardiovascular Events (MACE)
	
MACE (requiring adjudication as defined above) is defined as:
 
 • Vascular Death (including cardiovascular and cerebro-vascular causes excluding hemorrhagic deaths outside of the central nervous system) • Non-fatal myocardial infarction • Non-fatal stroke (subtypes: hemorrhagic stroke, ischemic stroke, undetermined stroke type) 
Where,
 
 • Vascular death should be captured as an Event on Adjudication - Death eCRF page with 	
Period 2 (Fisher’s exact test), Period 3 (Fisher’s exact test for Maintenance Dosing Period Primary Population): TEAE by maximum severity by PT within Category
 
Listing: TEAE

Special Safety Topic	Definition / Derivation	Analysis / Summary / Listing

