Depressions	Depression is defined using the PTs from the Depression and suicide/self-injury SMQ as specified in MedDRA (SMQ: 20000035, which includes the sub-SMQs: 20000037 [Suicide/self-injury] and 20000167 [Depression (excl suicide and self injury)]).	
Period 2 (Fisher’s exact test), Period 3 (Fisher’s exact test for Maintenance Dosing Period Primary Population): TEAE by PT within SMQ and sub-SMQ
 
Listing: TEAE

Inflammatory Bowel Disease (IBD)	
IBD will be identified using the following subcategory and MedDRA PTs. The narrow terms are considered IBD.
 
IBD Specific Terms (Narrow terms):
 
 • Inflammatory Bowel Disease: Inflammatory bowel disease • Crohn’s Disease: Crohn’s disease • Ulcerative Colitis: Acute haemorrhagic ulcerative colitis; Colitis ulcerative; Proctitis ulcerative 
Non-Specific Terms (Events That Can Occur with IBD (Broad Terms)): The PTs in this category are listed in the LY2439821 PSAP v8 Appendix 11 (or most current version).
	
Period 2 (Fisher’s exact test), Period 3 (Fisher’s exact test for Maintenance Dosing Period Primary Population): TEAE by PT within subcategory
 
Listing: TEAE

Interstitial Lung Disease (ILD)	
ILD is defined using the following terms:
 
 • Narrow terms in the Interstitial lung disease SMQ (20000042) • Additional 6 PTs from Eosinophilic pneumonia SMQ (20000157): 
 ○ Angiolymphoid hyperplasia with eosinophilia (Narrow) ○ Eosinophilic bronchitis (Narrow) ○ Hypereosinophilic syndrome (Narrow) ○ Loeffler’s syndrome (Narrow) ○ Pulmonary eosinophilia (Narrow) ○ Pulmonary vasculitis (Narrow) 	
Listing: TEAE

Abbreviations: AE = adverse event; AESI = adverse event of special interest; eCRF = electronic case report form; HLT = high-level term; PT = preferred term; SAE = serious adverse event; TEAE = treatment emergent adverse event.

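### The protocol has suspected inflammatory bowel disease adjudicated by an external committee, but the SAP classifies IBD by reported preferred terms and does not say how the committee's result is used, so the two counts may differ.

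*SAP*

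**What the plan says.** Protocol Section 10.3.1.1.1 includes IBD, meaning Crohn's disease and ulcerative colitis, among the adverse events of special interest. It sets a wide net: "Data on suspected IBD, as identified by events possibly indicative of ulcerative colitis and CD, will be collected". It then says "the events will be adjudicated by an external CEC made up of gastroenterologists with expertise in IBD". The purpose of adjudication is given in the same section: "The role of the CECs is to adjudicate defined clinical events, in a blinded, consistent, and unbiased manner".

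The IBD row of SAP Table RHBH.6.8 (Section 6.12.3.1) begins "IBD will be identified using the following subcategory and MedDRA PTs". It divides the terms into a narrow set (five preferred terms: IBD itself, Crohn's disease, and three ulcerative colitis or proctitis terms) and a broad set of non-specific terms, whose list is held in an appendix of the program safety analysis plan (PSAP). The case rule is "The narrow terms are considered IBD". The planned outputs are treatment-emergent events by preferred term inside each subcategory, with Fisher's exact test in Period 2 and in the Period 3 primary population, and a listing.

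The cerebro-cardiovascular row of the same table also concerns an externally adjudicated topic. There the rule is "Events will be analyzed using MedDRA PT nested within the CEC assessment".

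**The concern.** The trial sets up a blinded expert committee to decide which suspected events are IBD, and the SAP then writes a case rule that makes no use of the decision. Two kinds of disagreement are left unresolved. A site may report a narrow term that the committee does not accept; it still counts as IBD. A site may report a symptom or a non-specific bowel term that the committee judges to be IBD; it stays outside the IBD count.

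The question is a live one in this population, because the note to exclusion criterion [20] in Protocol Section 8.2 admits patients with a history of Crohn's disease or ulcerative colitis if they have been free of exacerbation for at least six months. At stake is whether the study report gives an IBD rate and a case list that can be reconciled with the committee's findings on an event of special interest.

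**Working it through.** The documents state no IBD rate, threshold or power, so there is no plan figure to reproduce. The check is a comparison of texts, followed by a small calculation of how much one reclassified event weighs.

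**Step 1. Compare the rows of SAP Table RHBH.6.8 that have an outside check on case status.**

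- Cerebro-cardiovascular events: adjudicated under Protocol 10.3.1.1.1. The SAP nests preferred terms within three committee outcomes (confirmed, not an event, documentation insufficient). The major cerebro-cardiovascular events row also draws on named adjudication eCRF pages.
- Opportunistic infections: no committee, but the SAP has a review step. Narrow terms can be overturned on medical review, and for the rest "Medical review of broad terms is needed for final determination of patients meeting the program definition of OIs".
- IBD: adjudicated under Protocol 10.3.1.1.1. The SAP row has neither committee outcomes nor a medical review step, and names no adjudication page.

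In the SAP, adjudication is used only for the cerebro-cardiovascular and major cerebro-cardiovascular rows.

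**Step 2. Cross the reported term with the committee's verdict.**

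- Narrow term, confirmed: counted as IBD by both.
- Narrow term, not confirmed: counted by the SAP, not by the committee.
- Broad term, confirmed: counted by the committee; the SAP tabulates it as non-specific.
- Broad term, not confirmed: counted as IBD by neither.

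The second and third cells move the count in opposite directions, so the sign of any difference cannot be predicted.

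**Step 3. Weight of one event.** The planned induction sizes in SAP Section 5.3 are 168, 168 and 84; pooled ixekizumab is 168 + 168 = 336.

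- One ixekizumab arm: 1/168 = 0.60 percentage points.
- Pooled ixekizumab: 1/336 = 0.30 points.
- Placebo: 1/84 = 1.19 points.

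**Step 4. Effect on the Fisher test.** The event counts here are assumed: k events in one ixekizumab arm of 168 and none in 84 on placebo.

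- k = 0: rate 0%, p = 1.00
- k = 1: rate 0.60%, p = 1.00
- k = 2: rate 1.19%, p = 0.55
- k = 3: rate 1.79%, p = 0.55

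For k = 2, the chance that both events fall on ixekizumab is (168 × 167)/(252 × 251) = 0.444 and that both fall on placebo is (84 × 83)/(252 × 251) = 0.110. The two-sided p is 0.444 + 0.110 = 0.55. With the pooled 336 against 84, p = 1.00 for every k from 0 to 3. At counts this low, moving one event changes the rate and the case list but not the result of the test.

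**The case against.** The strongest reply is that the SAP does what the protocol's analysis section asks. Protocol Section 12.2.8.1 says that adverse events of special interest will be investigated through groupings of MedDRA preferred terms. The protocol's list of these events attaches adjudicated endpoints to the cerebro-cardiovascular entry but not to IBD, and nowhere does it name the adjudicated count as the IBD analysis. This stands in part: the SAP omits a result that the protocol has produced, rather than contradicting a stated analysis. It does not remove the point, because the same sentence in Section 12.2.8.1 covers cerebro-cardiovascular events, where the SAP combines preferred terms with the committee's assessment.

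A second reply is that SAP Section 6.12.3.1 lets the PSAP supersede the SAP if the terms or the analysis change for a special safety topic. The PSAP was not available, so a reader should not infer that the operative plan never uses the adjudication. What can be said is that the SAP does not, and that its IBD row cites the PSAP only for the list of broad terms.

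A third reply is that no event under a listed term is lost: the broad terms are tabulated and the events are listed. That is correct. The missing piece is the verdict beside them.

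A reader might go further and infer that the SAP's IBD rate is wrong, or less accurate than the committee's. The documents do not show this. As a count of reported terms it is correct, and a confirmed-only count could itself miss true cases if documentation is insufficient, an outcome that the cerebro-cardiovascular scheme provides for.

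**Conclusion.** The mismatch between protocol and SAP is real and worth correcting, but modest. The SAP classifies IBD by reported term and leaves out the result of an adjudication that the protocol requires, so the reported count may differ from the committee's in either direction. One such difference is 0.6 percentage points of a planned arm of 168, or 0.3 of the pooled 336. The consequence is limited to the descriptive IBD rate and the case list. No primary or gated endpoint is involved, and for the assumed counts of 0 to 3 events the Fisher p-value stays at 0.55 or above.

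It is tempting to say that one reclassification could double or halve the IBD count. That holds only if the count is one or two, and the documents give no expected number. Nor does the cerebro-cardiovascular row support making confirmed events alone the main summary: it uses all events that qualify for adjudication, split by outcome.

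The conclusion assumes that the PSAP does not already cover adjudicated IBD. The percentages assume the planned enrolment.

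**What to change.** In the IBD row of SAP Table RHBH.6.8:

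- present all adjudicated IBD events by preferred term nested within committee assessment (confirmed, not confirmed, insufficient documentation), in the format of the cerebro-cardiovascular row;
- add the committee outcome to the IBD listing;
- keep the narrow-term and broad-term counts alongside, so that the two classifications can be reconciled.

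If the PSAP already specifies this, a cross-reference to the section is enough.

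The cost is one more table, one more listing column and a few lines of SAP text. The adjudication is already required by the protocol, so no new assessment of patients is needed. The SAP names no eCRF page for IBD adjudication, so the sponsor should confirm that the committee's results are held in a form that can be merged with the adverse event data.
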